8.3.3. Covariates

Patient demographics, clinical characteristics, comorbidities, and concomitant medications will be measured during baseline period and index date, and identified by Read Medical Codes,

Comparative Effectiveness and Safety of DOACs in Patients with AFib in the UK

ICD-10 diagnosis codes, and medication ATC codes for corresponding covariates. These covariates include cohort entry year, age, sex, socioeconomic indicators (e.g., marital status), and selected components of CHA₂DS₂ VASc stroke risk score^{27,28} (heart failure, hypertension, and diabetes), and ORBIT-AF bleeding risk score in AFib patients^{29,30} (heart failure, renal impairment, hepatic impairment; osteoporosis/hip fractures, anemia, antiplatelet therapy, aspirin therapy, NSAIDs therapy, and smoking and alcohol drinking history [if available]).

Additional comorbidities and concomitant medications deemed to be associated with the primary and secondary outcomes of interest will be included in the analyses. All covariates will be determined based on the literature and clinical knowledge. The operational definitions of each covariate will be recorded in the STaRT-RWE template and are available on request.

9. Data Analysis

Data analyses will be performed in a stepwise approach involving three distinct sequential phases (Figure 9.1): *Exploratory Phase* (data explorations will be done in advance to inform key design decisions), *Diagnostic Phase* (requirements that must be met prior to viewing study outcomes, e.g. covariate balance), and *Inferential Phase* (comparative analyses).

[figure not shown]

Figure 9.1 Data Analysis Phases

In the *Exploratory Phase*, the study implementation team completed explorations related to the patient selection criteria, exposure groups, and outcome definitions that informed the development of the study protocol.

For the *Diagnostic Phase*, the checklist in Table 9.1 must be satisfactorily completed prior to beginning the implementation of the *Inferential Phase*. As such, the relationship between the exposure and outcome of interest will not be described or evaluated in the analytic dataset until the study implementation team reaches consensus that the diagnostic criteria are satisfied.

Table 9.1 Diagnostic Checklist to Complete Prior to Progression to the Inferential Phase

Diagnostic Criteria	Description
Confirm adequate sample size	
Adequate sample size will be defined as the minimum sample size required to achieve 80% power to detect a HR of ≥ 0.80 for the primary outcome of stroke under the assumptions of 1:1 matching ratio of the primary comparators (apixaban vs. rivaroxaban); a false-positive rate $\alpha=0.05$; a 1-sided test; and a background stroke incidence rate of 47 events per 100,000 person-years in patients with AFib³¹
 
Note: If adequate sample size is not reached (i.e., minimum HR

Comparative Effectiveness and Safety of DOACs in Patients with AFib in the UK

	
that we can detect is <0.80), it will not solely prohibit us from moving on to interventional analysis. NICE would typically use treatment effect estimates to parameterise economic models and as long as the uncertainty in estimates is quantified, it can be accounted for in decision-making. In addition, a recent article³² deprioritized the importance of power calculations for observational studies, noting that observational analyses with imprecise effect estimates should be completed as small studies can be pooled to provide a more precise effect estimate. Therefore, this analysis is informative even if the sample size is insufficient to detect a HR ≥ 0.80 with 80% power.

Confirm positivity of variables	
Propensity score distributions will be visually inspected, and overlap in all areas of the propensity score distributions will be confirmed.
 
Other approaches, such as propensity score weighting, will be explored to achieve covariate balance in case propensity score matching is insufficient.

Confirm baseline confounder balance	
The distributions of all potential confounders will be confirmed to be balanced for each comparison of interest. Covariate balance will be defined as ASD ≤ 0.10.
 
Although covariates with balance prior to propensity score matching may be removed from the propensity score model, balance of these covariates will still be confirmed after matching. Covariates with small residual imbalance (defined as $0.10 \leq \text{ASD} \leq 0.15$) may be deemed balanced if the covariate does not predict the outcome among the referent group (defined as ASD < 0.10 when comparing the risk of the outcome in those with the covariate vs. those without it) Evaluation of imbalance in outcome prediction will only be conducted once at the end of the diagnostic phase if all other diagnostic criteria are met.

Confirm models are not overfit	All models must contain ≥ 12 exposed patients per covariate
Confirm persistence of treatment	
Initiators of DOACs stay on treatment for a substantial amount of time after starting treatment. The definition of "substantial persistence" will be finalized during the diagnostic phase and will be data driven.
 
If substantial crossover or censoring is observed, appropriate methods to account for these censoring issues will be applied in the comparative analyses.
 
Preliminary analyses show patients treated with DOACs in the database have a median follow-up of 2.3 years (IQR, 1.0-3.9). In clinical trials, the median duration of treatment was 1.5 years.

Unless otherwise specified, results will be provided as descriptive statistics with categorical variables reported using frequency distributions, and continuous variables reported using means, standard deviations, medians, minimums, maximums, 25th percentiles and 75th

Comparative Effectiveness and Safety of DOACs in Patients with AFib in the UK

percentiles. For inferential statistics, both crude and covariate adjusted analyses will be reported for study outcomes.

Among patients in each of the exposure groups, the incidence rates and 95% confidence intervals (CI) of stroke and secondary outcomes will be calculated for each of the mutually exclusive comparison groups, along with the number of events, total number of individuals, and accrued person-time. Incidence rates will be calculated as the number of incident outcomes of interest within the follow-up period divided by the total person-time at-risk, and reported as rate per 1,000 person-years.

In each comparison cohort, multivariable logistic regression will be used to estimate the probability of a patient's initiation of the exposure given baseline covariates and cohort entry year (i.e., the propensity score). Propensity score matching between exposure groups will be performed using 1:1 nearest neighbor matching without replacement with a maximum matching caliper of 0.01. In addition to graphical depictions of propensity score distributions, the absolute standardized differences (ASD) in proportions and means of baseline characteristics will be estimated to examine comparability of exposure groups. Covariates with $ASD \leq 0.10$ are considered balanced between comparator groups.³³ Covariates with small imbalances $0.10 \leq ASD \leq 0.15$ may be deemed balanced if the covariate does not predict the outcome among the referent group.

Cox proportional hazards regression (outcomes model) will be used to estimate hazard ratios (HR) and 95% CI for each outcome after propensity score matching. The incidence of stroke and secondary outcomes will be compared between individual DOACs in primary and secondary comparisons as mutually exclusive cohorts.

Subgroup analyses that will be considered include DOACs initiators with prior warfarin use; age (<75 and ≥ 75 years); concomitant aspirin use; CHA₂DS₂ VASc score (0-1, 2-3, and ≥ 4), and selected comorbid conditions, e.g. diabetes, heart failure, and BMI status (<30 and ≥ 30 kg/m²).

Sensitivity analyses will be performed to assess the impact of varying the study period on study findings by limiting analyses on data up to February 28, 2020 to account for potential impact of COVID-19 pandemic on healthcare utilization.

Additionally, high-dimensional propensity score (HdPS) analysis will be used as a sensitivity analysis to estimate the association between treatment with DOACs and the primary outcome of stroke. The HdPS approach is a 7-step algorithm that empirically identifies a pool of covariates from different data dimensions based on their prevalence, and then selects a subset of the covariates for inclusion in a propensity score model based on their potential to bias the exposure-outcome association.³⁰

Missing values will be reported as missing, and no imputation will be undertaken. All data analysis will be conducted using Aetion Evidence Platform® (2021), software for real-world data analysis. Aetion, Inc. <https://www.aetion.com>.

10. Limitations of the Research Methods

This study will be based on secondary use data from EHR with inherent limitations, including misclassification. For example, a patient may not necessarily use a medication that they have received a prescription for; however, this is less likely in the case of medications for chronic conditions like cardiovascular diseases. Additionally, while it is possible to identify study

Comparative Effectiveness and Safety of DOACs in Patients with AFib in the UK

outcomes of interest in the THIN® database, misclassification of the outcome is possible, as the presence of a diagnosis in medical records does not necessarily indicate a true presence of disease; however, the outcomes of interest are included in the Quality and Outcome Framework (QOF)³⁴ which rewards and incentivizes GPs in England for quality care and coding of diagnoses. In addition, validated algorithms from previously published real-world studies will be used to define study variables of interest.

An incident user design will be applied to reduce biases that can impact non-randomized studies, especially when using EHR.³⁵ An ITT analysis will be used because it has the advantage of eliminating certain types of biases by preserving the prognostic balance obtained through the propensity score matching and maintaining sample size;^{36,37} however, ITT analysis is sometimes considered to be “too conservative” and has the possibility of exposure misclassification.^{35,36} Additionally, “as-treated” approach will be used that will censor individuals upon discontinuation of index treatment or treatment crossover. However, limitations of an “as-treated” analysis include the possibility of introducing certain biases including differential and informative censoring, or time-dependent confounding biases.^{36,37}

Finally, while the THIN® database contains substantial information for inclusion/exclusion criteria and confounder control, medical conditions or a family history of medical conditions are only ascertainable where established diagnoses and procedures for those conditions exist. Additionally, some key covariates may not be available (unmeasured or imperfectly measured confounders), e.g. alcohol and smoking histories are not routinely recorded. Residual confounding by unmeasured variables will likely be present; however, efforts will be made to incorporate all potential confounding variables into the propensity score analysis to minimize impacts from unmeasured confounding, including the application of HdPS sensitivity analysis. Compared to conventional confounding adjustment methods, HdPS algorithm improves confounding control in situations when the variables are weak confounders that are weakly associated with exposure and themselves are associated with unmeasured confounders.³⁸

11. Quality Control

The study data to be used for the proposed analysis will be connected to the Aetion Evidence Platform (AEP), which will be used to perform all the analyses. The AEP is a data-handling technology, which allows for the analysis of large patient claims, EHR, and other transactional datasets by indexing patient data into a form that can be queried by an internal patient variable language. Data is minimally transformed at the point of connection to the AEP, thus the original format of the THIN® data is preserved. At the point of data connection to the platform some discard rules are applied. Patient events are excluded if there are no dates associated with them, or if the start date of the event is preceded by the end date of the event (e.g. discharge date precedes admission date for an inpatient event). Aetion IDs are assigned to THIN® patient IDs and a crosswalk file is kept as a protected file available upon request to authorized parties. The patient data is individual level patient data and will be analyzed within the AEP. Aggregated results will be exported from the platform in the form of tables.

THIN® data are loaded into the AEP after minimal processing into patient longitudinal timelines to enable representation of the original data and without any data loss. The following data checks are performed during the data connection process:

- Events are required to have a valid start date.
- Record counts are cross-checked for validation and compared to the original data counts.

Comparative Effectiveness and Safety of DOACs in Patients with AFib in the UK

- Enrollment information is processed and checked, and all fields and sample records are checked to ensure validity.

The process is implemented via a double-programming, rule-based approach that is flexible, automated, and scalable so that it can be reproduced when data is updated. Data processed through the data connector (coded by the Aetion Data Engineering team) are compared against data transformed independently to reproduce the data connector logic (coded by the Aetion Data Science team). Checks are performed first on a subset of data, then on the full data. This process ensures that customers are working with a scientifically valid data product when they perform analyses on the data using the AEP. Statistical analyses will be conducted using the validated AEP.

The Aetion Science Team will build measures for cohort inclusion/exclusion criteria, outcomes and covariates. All measures created, cohorts developed, statistical analyses implemented, and tables populated will undergo quality control review by at least one additional analyst or scientist under the supervision of the Senior Scientist. Quality control methods include checks for the validity and logical content of codes and checks for missing values and variables. In order to control for potential inconsistencies and errors, all variables will be tabulated. In addition, the distribution of values for each variable, including potential outliers, will be examined. This protocol will be strictly followed in the study implementation. However, variable definitions may undergo modification if determined to be scientifically sensible. All changes to this protocol will be documented in protocol amendments.

12. Protection of Human Subjects

This study will be conducted in accordance with applicable laws and regulations of the country where the study is being conducted, as appropriate. This observational, non-interventional study does not affect the treatment of the patients. The study is conducted in accordance with ethical principles that are consistent with the Declaration of Helsinki, International Conference on Harmonisation (ICH) Good Clinical Practice (GCP), Good Pharmacoepidemiology Practice (GPP), and the applicable legislation on non-interventional studies and/or observational studies.

The study concept was approved by the THIN® Scientific Review Committee on July 6, 2021.

13. Management and Reporting of Adverse Events/Adverse Reactions

This is a non-interventional study using only structured secondary data, and attribution of adverse reactions/adverse events to specific exposure is not possible, and therefore no individual case safety report (ICSR) reporting is required. During the course of observational research using existing secondary databases, the proposed study will use structured data fields only and will not involve chart review or validation to obtain additional information on the adverse events other than the study outcomes of interest.

14. Plans for Disseminating and Communicating Study Results

This study protocol will be registered in the ENCePP EU PAS Register³⁹ prior to the implementation of the diagnostic phase. In addition, study findings will be disseminated as manuscript(s) in peer-reviewed journals and/or as conference abstract presentations at international professional conferences.

Comparative Effectiveness and Safety of DOACs in Patients with AFib in the UK

15. References

1. NICE. NICE strategy 2021 to 2026 [Internet]. 2021 [cited 2021 Jun 24]. Available from: <https://www.nice.org.uk/about/who-we-are/corporate-publications/the-nice-strategy-2021-to-2026>
4. European Medicines Agency (EMA). Human Medicines European Public Assessment Report (EPAR). January 2021. Available from: <https://www.ema.europa.eu/en/medicines>. Accessed August 25, 2021.
5. Electronic Medicines Compendium (EMC). Authorized Medicines in the UK. June 2021. Available from: <https://www.medicines.org.uk/emc/product/6907/smpc#AUTHDATE>. Accessed August 25, 2021
6. National Institute for Health and Care Excellence (NICE). Atrial Fibrillation Management Guidelines. June 2014. Available from: <https://www.nice.org.uk/guidance/cg180>. Accessed August 25, 2021

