6.3. Secondary Objectives

The secondary objectives are to:

- Estimate the incidence rates and analogous hazard ratios of stroke (ischemic or hemorrhagic) for patients with nonvalvular AFib who initiated:
 - apixaban compared to edoxaban, dabigatran, and DOACs class
 - rivaroxaban compared to edoxaban, dabigatran, and DOACs class
 - edoxaban compared to DOACs class
 - dabigatran compared to DOACs class
- Estimate the incidence rates and evaluate the analogous hazard ratio of all-cause mortality, myocardial infarction (MI), transient ischemic attack (TIA), major bleeding events, and major adverse cardiovascular events (MACE) for patients with nonvalvular AFib who initiated individual DOACs compared to those who initiated other DOACs (see Table 6.1).

7. Data Source

This study uses anonymized patient RWD from The Health Improvement Network (THIN®) Database (A Cegedim Proprietary Database). THIN® is an unobtrusive medical data collection scheme that collects anonymised patient data from its members. THIN® data is a primary care research database containing anonymised electronic health record data from around 850 UK general practices (GPs) using the VISION clinical system (since 1994), containing records around 20 million patients, of which 2.6 million are currently active. THIN® collates the computerized medical records of general practitioners (GPs) in the UK who act as the gatekeepers of healthcare and maintain patients' life-long electronic health records. As such they are responsible for primary healthcare and specialist referrals, and they also store information stemming from specialist referrals, and hospitalizations. GPs act as the first point of contact for any non-emergency health-related issues, which may then be managed within primary care and/or referred to secondary care as necessary. The THIN® database includes demographic, medical diagnosis, patient medical history, lifestyle factors, and written prescription information on individual patients. The Quality and Outcome Framework (QOF) rewards practices for the quality care they provide their patients, based on a number of indicators, including medical record data entry.

The THIN® database has been used for scientific publications in AF and stroke research²²⁻²⁵ and has been validated and widely used in pharmacoepidemiologic studies.²²

8. Research Methods

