8.2.1.2. Exclusion Criteria

The following are the exclusion criteria for the study cohort:

- Exclusion criteria applied during selection of the data cut:
 - <1 diagnosis code for AFib on index date or in 12 months prior (applied during selection of the data cut)
 - <1 risk factor for stroke other than Afib on index date or in 12 months prior defined by CHA₂DS₂ VASc >1 for men and >2 for women²⁶
 - <1 medical encounter in the 180 days prior to index date
 - ≥1 diagnosis code for the following conditions on index date or any time prior:
 - Cardiac valve disease (mitral stenosis, valvular replacement)
 - Deep vein thrombosis
 - Pulmonary embolism
- Exclusion criteria applied after selection of the data cut:
 - <18 years of age on index date
 - <12 months' registration with a GP prior to the index date
 - ≥1 prescription record for DOACs in the 12 months prior to the index date (i.e., prevalent users)
 - ≥1 diagnosis code for the study outcomes of interest (stroke, MI, TIA, major bleeding events) on index date or any time prior
 - ≥1 diagnosis code for the following conditions on index date or any time prior:
 - Angina
 - Congenital heart disease
 - Missing age
 - Missing gender

Comparative Effectiveness and Safety of DOACs in Patients with AFib in the UK

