8.2.2. Study Periods

The study observation period spans July 1, 2013 through December 31, 2020, consisting of a drug indexing, baseline and follow-up periods (Figure 8.1). The drug indexing period will be used to ascertain DOACs initiation (index date). Baseline period is defined as 12 months prior to and including the index date. The follow-up period will include all available time after study index date. Patients will be followed in an “intention to treat” (ITT) approach from their index date until the end of follow-up period or the occurrence of the following events, whichever occurs first:

- First occurrence of the study outcomes of interest
- Death
- End of patient data
- End of patient registration with GP.

In addition, patients meeting the selection criteria will be followed in an “as-treated” approach from their index date until the end of the study follow-up period or the occurrence of the following events, whichever occurs first:

- First occurrence of the study outcomes of interest.
- Death
- End of patient data.
- End of patient registration with GP.
- Termination of exposure, crossover of exposure group, or addition of another DOAC.

Termination of exposure in the as-treated analysis is defined as having a gap exceeding 30 days (grace period) between the end of a prescription, based on its start date and duration, and the start of the next prescription, or if no additional prescription occurs. The termination date is defined as the prescription end date plus a 30-day risk window.

Comparative Effectiveness and Safety of DOACs in Patients with AFib in the UK

[figure not shown]

Figure 8.1 Study Design Diagram

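### Chronic comorbidities are measured only in the 12 months up to index although longer history is used elsewhere; conditions not re-recorded in that window would count as absent, and the balance check could not show it.

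*Protocol*

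**What the plan says.** Section 8.3.3 gives one measurement rule for every type of covariate: "Patient demographics, clinical characteristics, comorbidities, and concomitant medications will be measured during baseline period and index date". Section 8.2.2 fixes the length: "Baseline period is defined as 12 months prior to and including the index date". The covariates under this rule include "heart failure, hypertension, and diabetes" from the stroke risk score. They also include renal and hepatic impairment, osteoporosis or hip fracture, and anaemia from the bleeding risk score.

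Other sections treat history differently:

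- Section 7 describes the source as holding patients' "life-long electronic health records".
- Section 8.2.1.2 excludes valve disease, deep vein thrombosis, pulmonary embolism, prior outcome events, angina and congenital heart disease on codes found "on index date or any time prior". The last three are applied after the data cut has been selected.
- The same section judges stroke-risk eligibility on the short window: "<1 risk factor for stroke other than Afib on index date or in 12 months prior". This is applied while the data cut is being selected.
- The registration criterion excludes patients with "<12 months' registration with a GP prior to the index date". Twelve months is therefore a minimum, and longer history is not barred.

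Under section 9, the covariates feed the propensity score. Table 9.1 requires an absolute standardised difference (ASD) of at most 0.10, and lets covariates already balanced before matching be left out of the model. No analysis varies the look-back window.

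**The concern.** In a GP record, a chronic diagnosis may be entered once and not again. If no further code falls in the 12 months before index, the rule treats the patient as free of the condition, even though the diagnosis is in the record. The protocol relies on all prior history to decide who is excluded but not to control confounding, and it gives no reason for the difference.

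Two consequences follow. First, matching balances the recorded version of the confounder. Among patients recorded as free of the condition, the arm with the higher true prevalence still holds more unrecorded cases. This happens even when under-recording is equal in both arms. Second, the balance check uses the same recorded variable, so it can be met while the true condition remains unbalanced. Under-recording also shrinks the imbalance seen before matching, which makes it easier to drop the covariate from the model. Any diabetes or heart failure subgroup defined by the same window would carry the same error.

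**Working it through.** The protocol states no figure that depends on the window, so there is nothing of its own to reproduce. What follows is an illustration.

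**Inputs, all assumed because the protocol gives none.** One binary confounder; true prevalence pA = 0.40 and pB = 0.30; risk ratio for stroke 2; no false-positive codes; the window captures a share s of true cases, equal in both arms; perfect matching on the recorded variable; no other covariate related to the condition.

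**Formulas.**

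- True prevalence among those recorded absent, per arm: q = p(1 − s)/(1 − p·s).
- Recorded prevalence in both arms after matching, set to arm B's: m = 0.30·s.
- True prevalence after matching, per arm: t = m + (1 − m)·q.
- Residual bias ratio: (1 + tA)/(1 + tB).
- ASD = |tA − tB| / √{[tA(1 − tA) + tB(1 − tB)]/2}.

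**Before matching.** Bias = 1.40/1.30 = 1.077; true ASD = 0.21.

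**Worked case, s = 0.7.** qA = 0.40 × 0.30/(1 − 0.28) = 0.167. qB = 0.30 × 0.30/(1 − 0.21) = 0.114. m = 0.21. tA = 0.21 + 0.79 × 0.167 = 0.342 and tB = 0.300. Bias = 1.342/1.300 = 1.032. The share of the log-bias left is ln 1.032/ln 1.077, or 43%.

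| Capture s | tA | tB | Residual bias ratio | Share of log-bias left | Recorded ASD | True ASD |
|---|---|---|---|---|---|---|
| 1.0 | 0.300 | 0.300 | 1.000 | 0% | 0 | 0 |
| 0.9 | 0.316 | 0.300 | 1.012 | 16% | 0 | 0.03 |
| 0.7 | 0.342 | 0.300 | 1.032 | 43% | 0 | 0.09 |
| 0.5 | 0.363 | 0.300 | 1.048 | 63% | 0 | 0.13 |
| 0.3 | 0.380 | 0.300 | 1.061 | 80% | 0 | 0.17 |

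The 0.10 limit is exceeded unseen at 50% capture or less, but not at 70% or more.

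**A smaller true difference.** With 30% against 25%, the true ASD before matching is 0.112. The recorded ASD before matching is 0.104, 0.089, 0.073 and 0.055 at s = 0.9, 0.7, 0.5 and 0.3. If the covariate stays in the model (m now set to the mean recorded prevalence of the two arms), the true ASD after matching is 0.015, 0.042, 0.065 and 0.086. It stays below 0.10 throughout, so the check would give the right answer. At 70% capture or less, however, the covariate looks balanced before matching and may be left out of the model. The true imbalance of 0.112 would then not be matched on directly.

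**The case against.** **The loss may be small.** Harm needs chronic diagnoses not to be re-recorded within 12 months, and the protocol gives no re-recording rate. Some of its text points the other way. Section 7 says a quality incentive scheme rewards data entry. Section 8.2.1.2 requires a medical encounter in the 180 days before index and an AFib code within 12 months, so these are recently seen patients. This stands. A reader might infer that a patient with diabetes coded five years ago is necessarily entered as not diabetic. The text supports that only if no later code falls in the window.

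**Other covariates help.** Concomitant medications are measured in the same 12 months. Drugs for diabetes, hypertension or heart failure would partly stand in for a missing diagnosis code. This also stands, and it makes the single-confounder figures too large where such proxies exist.

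**The protocol admits the problem.** Section 10 accepts imperfectly measured confounders and likely residual confounding, and points to the high-dimensional propensity score analysis. This stands in part. The limitations do not mention the window, and that analysis covers only the primary outcome, with no longer look-back stated.

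**A fixed window gives equal look-back.** Only 12 months of registration is guaranteed. If usable history began with the observation period on 1 July 2013, look-back would run from 12 months for the earliest initiators to seven and a half years for the latest. It could then differ by drug as uptake changed over time. This is a real cost of a longer window. The protocol does not offer it as a reason, however, and does not apply it to the exclusions.

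**The template may differ.** Operational definitions sit in the STaRT-RWE template, which is not shown and might set longer windows for some covariates. Section 8.3.3 does not say so.

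**Conclusion.** The concern holds as a conditional weakness. A stated rule sets aside diagnosis history that the study already uses for exclusions, and the planned balance check cannot reveal what is lost. The size cannot be stated from the protocol. Under the assumed inputs the residual bias is about 3% to 6% at 70% to 30% capture, and about 1% at 90%. It is lower still where medication covariates act as proxies. It could add up if several confounders were affected in the same direction.

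Three stronger readings are not supported. The protocol does not show that long-standing conditions are in fact missed. It does not show that the balance check will fail, since with the smaller assumed difference the check was right at every capture rate tried, provided the covariate stayed in the model. Nor does it show that subgroup patients are misassigned: section 9 lists subgroups only as ones to be considered, and gives no window for them. This is an avoidable limit on confounding control that is cheap to remove, not a demonstrated error in the result.

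**What to change.** - Define chronic comorbidity covariates, and any diabetes or heart failure subgroups, from all available history up to and including the index date.
- Keep 12 months for medications, encounters and acute conditions.
- Include length of prior registration in the propensity score, because look-back will vary by patient and calendar time. Cohort entry year is already in the model.
- Run the 12-month version as a sensitivity analysis, and report the prevalence of each chronic condition under both windows. That gives a direct view of how much the short window misses.
- State whether the CHA2DS2-VASc eligibility window stays at 12 months. It was set when the data cut was selected, so patients whose risk factors were not re-recorded may already be outside the data. Whatever is decided, use one consistent look-back for the CHA2DS2-VASc subgroups and say which.
- If the STaRT-RWE template already uses longer windows for chronic conditions, say so in section 8.3.3.

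The cost is re-specifying look-back windows in existing measures, one added covariate and one added sensitivity analysis. Changing the eligibility window would probably need a new data cut and is not required for the rest.

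### The adequate-sample-size criterion uses an unexplained 1-sided 0.05 test, while the primary hazard ratio is reported with a conventional 95% CI; a matching criterion needs 27% more strokes

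*Protocol*

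**What the plan says.** The sample-size row of Table 9.1 (protocol, Section 9) defines adequacy as the "minimum sample size required to achieve 80% power to detect a HR" of 0.80 (printed with a ≥ sign) for stroke. The stated assumptions are a "1:1 matching ratio of the primary comparators (apixaban vs. rivaroxaban"), a false-positive rate of 0.05, "a 1-sided test; and a background stroke incidence rate" of 47 events per 100,000 person-years. The row prints no number of patients, strokes or person-years. Its note adds that a size shortfall, described as a smallest detectable HR below 0.80, does not by itself prevent the comparative analysis.

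The analysis text of the same section says that Cox regression "will be used to estimate hazard ratios (HR) and 95% CI for each outcome after propensity score matching", and that "the incidence rates and 95% confidence intervals (CI) of stroke and secondary outcomes will be calculated" for each comparison group. Section 6.2 states the primary objective as estimating stroke incidence rates and the hazard ratio for apixaban compared with rivaroxaban. It names no expected direction.

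**The concern.** The sidedness in Table 9.1 is the only one-sided element in the protocol. A 1-sided test at 0.05 corresponds to a 90% CI or a one-sided 95% bound, and neither is planned. A 95% CI given without qualification is conventionally two-sided, with 2.5% in each tail. The 80% in the criterion therefore describes a less demanding standard than the interval that readers will be shown.

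Section 5.3 frames the clinical question as which agent has the best benefit-risk profile within the class, so a difference in either direction would matter.

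The adequacy label also matters beyond this one study. Section 5 says that one purpose of such projects is to learn how long after launch the sample becomes large enough for comparative effectiveness work. A threshold set on a 1-sided basis declares the data large enough sooner than the reported interval would justify.

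**Working it through.** **Inputs.** From Table 9.1: HR 0.80, so |ln 0.80| = 0.22314 and its square is 0.049793; 1:1 matching; power 80% (z = 0.8416); alpha 0.05, 1-sided (z = 1.6449); background rate 47 per 100,000 person-years. From the analysis text of Section 9: 95% CI, read as two-sided (z = 1.9600).

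**Step 1: the criterion as written.** The protocol gives no event count to reproduce, so the criterion is converted to required strokes with the Schoenfeld formula for equal groups, D = 4(z_α + z_β)² / (ln HR)².

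- D = 4 × (1.6449 + 0.8416)² / 0.049793 = 496.7, so 497 strokes.
- Check: √(497/4) × 0.22314 − 1.6449 = 2.4873 − 1.6449 = 0.8424, and Φ(0.8424) = 80.0%. The criterion is coherent on its own terms.

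**Step 2: a criterion matching the reported interval.**

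- D = 4 × (1.9600 + 0.8416)² / 0.049793 = 630.5, so 631 strokes.
- Ratio: 631/497 = 1.27.

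**Step 3: 497 strokes judged by the 95% CI.**

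- Power for the interval to exclude 1 at HR 0.80: Φ(2.4873 − 1.9600) = Φ(0.5273) = 70.1%.
- HR detectable with 80% power: exp(−2.8016 / √(497/4)) = exp(−2.8016 / 11.147) = 0.778.

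**Step 4: check with another formula.** Freedman's formula, D = [(1 + HR)/(1 − HR)]² (z_α + z_β)², has the multiplier (1.8/0.2)² = 81. It gives 501 strokes (1-sided) and 636 (two-sided). Power at 501 strokes by the 95% CI is again 70.1%.

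**Step 5: what depends on the assumed rate.** Take 47 per 100,000 in the referent group and 0.8 times that in the other. The average rate is 0.00047 × 0.9 = 0.000423 per person-year.

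- As written: 497 / 0.000423 ≈ 1.17 million person-years.
- Two-sided: 631 / 0.000423 ≈ 1.49 million person-years.

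A cohort with exactly 1.17 million person-years has 497 strokes only if the rate is 47. It would reach 631 strokes, and so 80% power by the 95% CI, if the referent rate were about 47 × 631/497 ≈ 60 per 100,000. The 27% ratio of required events does not depend on the rate. The 70% for a cohort that just meets the criterion does.

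**The case against.** The best reply is that the study is about estimation. Section 6.2 asks for rates and a hazard ratio, Section 9 states no rule that success means a 95% CI excluding 1, and the note in Table 9.1 says that imprecise estimates remain useful if their uncertainty is quantified. The 1-sided test is also disclosed beside the 80%, so nothing is hidden. Sections 6 and 6.1 speak of reducing stroke, which has a directional flavour. All of this stands, and it limits the consequence. It does not supply a reason for the 1-sided test: the wording about reducing stroke never says that apixaban is expected to be better. The note deals with a cohort that falls short, whereas the mismatch concerns one that is labelled adequate. If precision is to be judged through the reported interval, the benchmark should use that interval.

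Three stronger readings are tempting but not supported:

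- A reader might infer that the study has 70% power where 80% was promised. The protocol prints no cohort size or stroke count, so actual power cannot be stated.
- A reader might infer that any cohort that just meets the criterion has 70% power whatever the stroke rate. Adequacy is defined as a size under an assumed rate, so a higher true rate would give more strokes and more power.
- A reader might infer that the criterion decides whether the analysis goes ahead. The note says that a shortfall alone does not.

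**Conclusion.** The mismatch is real and stated within the protocol itself; it is not a detail left to a later analysis plan. The criterion's 80% belongs to a 1-sided 0.05 test that is not justified, while the primary result is shown with a 95% CI for a comparison without a stated direction. Matching the two raises the requirement from 497 to about 631 strokes. A cohort of exactly 497 strokes would have about 70% power by the reported interval and a detectable HR of about 0.78. By the protocol's own description of a shortfall (smallest detectable HR below 0.80), that cohort counts as adequate on the 1-sided basis and as short on the two-sided one.

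This rests on reading the unqualified 95% CI as two-sided, on HR 0.80 as the target, on proportional hazards and 1:1 groups, and, for the 70%, on the assumed rate being the true one. The consequence is a mislabelled adequacy threshold and detectable HR. No estimate, interval or cohort changes.

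**What to change.** In the sample-size row of Table 9.1, replace the 1-sided test with a two-sided test at 0.05 (equivalently one-sided 0.025), state the requirement as about 631 strokes for HR 0.80 at 80% power, and report the detectable HR on that basis.

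If the 1-sided criterion is kept, give the reason for the direction and state beside it that 497 strokes provide about 70% power by the reported 95% CI.

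Either way the cost is a short edit and a somewhat less favourable figure. No extra patients or data are needed, because the analysis proceeds even if the criterion is missed.
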